Study Procedures – Because there may be significant heterogeneity in dialysis facilities and patient and staff populations across the 18 participating ESRD Networks, we will randomize dialysis facilities that were not included in formative testing within each ESRD Network region to either the multicomponent intervention (feedback report, webinar, and videos) or comparison group (usual care plus UNOS educational brochure). At baseline (Year 2, Q3-Q4), all eligible dialysis facility Medical Directors in both the intervention and control group will receive an email from their ESRD Network Executive Director a web-based survey (HIPAA-compliant surveymonkey) with informed consent. For those who consent to participate (in reporting secondary outcome measures), baseline surveys will then be administered. Within one week of this email (or immediately after for those that complete a baseline survey), all facility Medical Directors from participating facilities will be emailed a UNOS pamphlet and instructed to share with staff; intervention facilities will be emailed facility-specific performance feedback report and videos, and information about the educational webinar. At 3 months, all facility Medical Directors who consented to participate will be emailed follow-up surveys by their respective ESRD Network Executive Director to assess secondary outcomes. Our prior work has shown >90% response rates by Medical Directors when surveys are mailed directly from the ESRD Network.⁵³ Medical Directors will be offered an electronic gift card incentive (\$10) for participation.

Effectiveness Measure Outcomes – To test the effectiveness of this intervention, several outcomes will be assessed via surveys and surveillance data. Waitlisting data from 1 year post-intervention will be assessed using nationally available Dialysis Facility Report surveillance data in order to assess disparity reduction at the facility level. Follow-up surveys will be emailed to all Medical Directors at 3 months to test change in knowledge about the kidney allocation policy and whether Medical Directors have implemented

any staff training regarding the allocation policy within their dialysis facility, what methods the facility has used to educate ESRD patients about the kidney allocation policy, and whether the policy influenced facility Medical Directors' intent to refer more patients for transplantation.

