Measures are described below. Surveys will be pilot tested in formative phases and finalized with approval by the Dissemination Advisory Board.

1) Change in Waitlisting Disparity (Primary Outcome) – We will calculate facility racial disparity in waitlisting one year prior and post-intervention as the difference between the proportion of AA vs. whites waitlisted.

2) Change in Knowledge about the Kidney Allocation System (Secondary Outcome) – We will survey Medical Directors using a 20-question scale measuring knowledge about the kidney allocation system, and general transplant knowledge, based on a validated scale we have used among dialysis staff and patients.⁵⁴

3) Change in Staff Training about Kidney Transplant and the Allocation System (Secondary Outcome) – We will assess at baseline whether Medical Directors have trained their staff about transplantation and/or the details of the kidney allocation policy. We will ask whether the Medical Director provided training about transplant or the kidney allocation policy in the prior 3 months after intervention delivery, and information about training (e.g., did they hold a training session, send an email, watch video presentations, etc.). Details about trainings will be collected to inform best practices for staff training for future scale-up.

4) Evidence of Communication to Patients (Secondary Outcome) – To ensure that dialysis facility Medical Directors communicate information about the kidney allocation system to their staff and patients, we will track the educational video website usage by asking users to input user type, facility name, and location. This will allow us to track intervention dose and usage statistics such as number of uses by facility, time in application, etc. We have previously tracked other mobile educational initiatives through Google Analytics with success.⁵⁵

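### Materials are sent within a week whether or not the baseline survey is done, and no rule stops later answers counting as baseline, so measured change in the survey outcomes may be diluted

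*Combined protocol and SAP*

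**What the plan says.** Under Study Procedures, Medical Directors in both arms are emailed a web survey with consent. The baseline survey is for consenters: "For those who consent to participate (in reporting secondary outcome measures), baseline surveys will then be administered". The timing of the materials follows: "Within one week of this email (or immediately after for those that complete a baseline survey"). In both arms, "all facility Medical Directors from participating facilities will be emailed a UNOS pamphlet and instructed to share with staff". In addition, "intervention facilities will be emailed facility-specific performance feedback report and videos, and information about the educational webinar".

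The only calendar bound on this stage is "At baseline (Year 2, Q3-Q4"). Later, "At 3 months, all facility Medical Directors who consented to participate will be emailed follow-up surveys".

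The survey outcomes are defined as changes, for example "Change in Knowledge about the Kidney Allocation System (Secondary Outcome"), measured on a 20-question scale. Statistical Analyses says only that change in each secondary outcome will be examined. The protocol gives no closing time for the baseline survey, does not make dispatch wait for completion, and has no rule for a baseline returned after dispatch.

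**The concern.** The parenthesis in the dispatch sentence only makes sense if there are two groups: directors who complete the survey and get the materials at once, and directors who have not completed it and get them within the week regardless. For the second group, the dispatch rule lets exposure come before the baseline measurement.

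The intervention is meant to raise what the survey measures. A director who reads the report or watches a video of about five minutes and then answers the knowledge questions gives a baseline that already contains part of the effect. Subtracting it from the 3-month value understates the change. Late control baselines follow only the pamphlet, so the contrast between arms shrinks to the extent that the intervention does more, or does it sooner, than the pamphlet.

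At stake is the trial's evidence on whether directors' knowledge and reported practice changed. These outcomes are also Adoption measures in the RE-AIM table and feed the crude implementation index. Whether the index would inherit the problem depends on whether it is built from change scores, which the protocol does not state.

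**Working it through.** **No figure in the plan to reproduce.** Sample Size and Power covers the waitlisting disparity ratio only. The protocol gives no effect size, standard deviation, sample size or power for any survey outcome.

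**Which outcomes are exposed**

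| Outcome | Source | Exposed to late baselines? |
|---|---|---|
| Waitlisting disparity (primary) | Surveillance data | No |
| Communication to patients | Website tracking | No |
| Knowledge | Survey, change | Yes, mainly: it can move as soon as the materials are read |
| Intent to refer | Survey, baseline and 3 months | Less: it rests on estimated proportions of patients |
| Staff training | Survey, baseline and 3 months | Less: training takes time to arrange |

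**Dilution.** Let E be the true between-arm difference in change at 3 months. None of the following inputs is in the documents; all are assumed:

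- f: share of baselines answered after dispatch, taken as equal in both arms;
- g: share of E already present in late intervention-arm baselines;
- h: pamphlet effect already present in late control baselines, as a share of E.

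Late answers raise the mean intervention baseline by f·g·E and the mean control baseline by f·h·E. So

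measured difference = E − f·g·E + f·h·E = E·[1 − f(g − h)].

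**Illustrative power.** Write k for the bracket. A comparison that would have 80% power at two-sided 0.05 with clean baselines has power of about Φ(2.80·k − 1.96), since 1.96 + 0.84 = 2.80. The 80% is a reference point chosen here. Example: f = 20%, g = 0.5, h = 0 gives k = 1 − 0.20 × 0.5 = 0.90; 2.80 × 0.90 − 1.96 = 0.56; Φ(0.56) = 71%.

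With h = 0:

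| f | k (g = 0.25) | Power | k (g = 0.5) | Power | k (g = 1) | Power |
|---|---|---|---|---|---|---|
| 10% | 0.975 | 78% | 0.95 | 76% | 0.90 | 71% |
| 20% | 0.95 | 76% | 0.90 | 71% | 0.80 | 61% |
| 30% | 0.925 | 74% | 0.85 | 66% | 0.70 | 50% |

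**If the pamphlet also acts early.** With h = 0.25, the case f = 20%, g = 0.5 gives 1 − 0.20 × 0.25 = 0.95 instead of 0.90. With g = h there is no dilution at any f. With f = 0, which is what a cut-off at dispatch enforces, k = 1.

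**The case against.** The strongest reply is that the defect is inferred from silence. The paragraph describes a sequence of survey, baseline, then materials, and the one-week mark can be read as the end of the baseline window. Nowhere does the protocol say that an answer given after dispatch counts as a baseline. Surveys are still to be piloted and finalised, and administration details may sit in the IRB submission. This stands in part: the supportable statement is that no cut-off is given, and a reader who infers that late baselines will certainly occur and be used goes further than the text. It does not remove the point, because the dispatch rule is explicit, exposes non-completers on a fixed clock, and is paired with an analysis of change that has no rule for late answers.

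Three other stronger readings are tempting and not supported:

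- **That each survey stays open for two quarters.** The Year 2, Q3-Q4 entry may only be the roll-out calendar across 18 Networks; the one-week clock runs from each director's email.
- **That power falls to 71%, 61% or 50%.** Those figures need the whole 3-month effect to be present at the late baseline and no pamphlet effect. That is hard to believe for training, which follow-up asks about over the 3 months after delivery, or for estimated referral proportions.
- **That the main result is at risk.** Waitlisting comes from surveillance data.

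The response rate above 90% cited from prior work does not settle the matter either way, because nothing is said about when responses arrived.

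It is also fair to say that any bias is towards no effect, on secondary outcomes only, and that randomisation allows 3-month values to be compared directly. This limits the severity. It also points to the remedy, but the protocol describes the analysis as one of change.

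**Conclusion.** The point holds as a minor one. Followed as written, the dispatch rule can put post-exposure answers into the baseline, and nothing in the protocol prevents or handles this. The direction is towards no effect, provided the intervention acts sooner or more strongly than the pamphlet (g greater than h). Knowledge is the outcome mainly exposed.

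The size cannot be fixed from the documents. For 10% to 30% late baselines and h = 0, the measured difference is 0.95 to 0.85 of the true one if half the effect is present early, and 0.90 to 0.70 if all of it is. It is near 1 if few directors answer late, and exactly 1 if g = h. The power figures only illustrate these factors from an assumed 80%.

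**What to change.** 1. Close each facility's baseline survey when its materials are sent, in both arms and after the same interval. Record completion and dispatch times.
2. Treat any answer given after dispatch as a missing baseline.
3. Analyse each survey outcome as the 3-month value by randomised arm, adjusted for the pre-dispatch baseline.
4. Name the method for missing baselines: a missing indicator, or imputation of the mean baseline pooled over both arms. Ordinary baseline-adjusted regression would drop these directors. Either simple method is valid here because whether the baseline is missing is settled before exposure, provided that the survey email does not reveal the arm. All 3-month responders then contribute.
5. Consent comes with the same emailed survey, so state whether a director may still consent after the cut-off. Otherwise closing the survey could also remove that director from the 3-month survey.

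The cost is a survey setting, two recorded times and a few sentences in the analysis section. Some baseline responses are lost, up to the share that would have been late (f above), with some loss of precision in the adjustment. Cheap improvement.

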The public health burden of kidney failure in the United States is substantial, with more than 600,000 end-stage renal disease (ESRD) patients. There are two main treatments for kidney disease – dialysis or kidney transplantation. A complex, multi-tiered national system regulates kidney disease care, reimbursement, and transplantation, creating barriers to overcoming the significant racial disparities that exist in transplantation, the most effective treatment for ESRD. The federal Organ Procurement and Transplantation Network of the United Network for Organ Sharing oversees the allocation of all deceased donor organs in the US, and on Dec. 4, 2014, a major change to the allocation policy was implemented that is expected to impact racial disparities in transplantation access. We propose to study the impact of the natural experiment offered by enactment of this new kidney allocation policy on reducing disparities in the key steps of referral for transplant evaluation, waitlisting, and transplantation, each of which have complexities for measurement at the local and national level. Based on national data that we have used to develop a systems-level practice, we will disseminate a systems-level practice of providing feedback to dialysis centers about their transplant performance to improve overall waitlisting rates and decrease disparities in kidney transplantation.

Within the Southeastern US, where access to kidney transplantation is the lowest and racial and socioeconomic disparities in transplant access are the most substantial, we will work with our Dissemination Advisory Board, which includes relevant stakeholders within the kidney health care system, to finalize intervention materials (Objective 1) and then disseminate dialysis facility-specific performance feedback reports as part of a multicomponent intervention (educational videos for staff and patients; webinar for staff) using a clinical effectiveness-implementation study⁵⁰ design among a national sample of 1500 dialysis facilities with racial disparities in waitlisting access (Objective 2). Key outcomes will include 1-year disparity reduction in dialysis facility-level waitlisting (primary outcome), and change in knowledge, intent to refer for transplant, communication to patients, and staff training about the allocation policy (secondary outcomes).

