Eligibility Criteria and Description of Potential Study Population – Facilities with at least n=11 patients (at least 4 AA patients) in their facility with a waitlisting disparity will be eligible for participation, since measured outcomes focus on disparity reduction and facilities with small proportions of AA or a small number of patients may be difficult to classify as a disparity facility. Of the facilities in the 18 ESRD Networks, n=1529 dialysis facilities had a racial disparity in waitlisting in 2014. Demographics of participating facilities with a racial disparity in waitlisting are: AA (42.3%) and 53.0% white; mean age 61.7 years; 65.5% unemployed, 11.4% Medicaid insurance; and 25.8% of patients waitlisted, and mean number of staff / facility 17.7. We expect ~1% of facilities will close in 1 year or there may be an improvement in racial disparities (from 2011) once we start the study, thus we expect a minimum of N=750 facilities will participate.

STUDY DESIGN AND METHODS

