5) Change in Intent to Refer Patients to Kidney Transplantation (Secondary Outcome) – We will assess the current referral practices of facilities by surveying Medical Director about the estimated proportion of patients interested, eligible, and referred for transplant in their facility at baseline and at 3 months post- intervention. We will ask questions about the estimated % of patients referred for transplant by specific patient characteristics (e.g. age, race/ethnicity, SES, time on dialysis, etc). A similar survey has been used in our Network in the past⁵³ and will be finalized by the Dissemination Advisory Board in objective 1. Obtaining actual referral data is only possible for ESRD Network 6 dialysis facilities. However, our prior analyses examining dialysis staff-reported referrals and actual referrals to transplant centers show high correlation ($r=0.79$; $p<0.01$).

Implementation effect measures: We will use an adaptation of the RE-AIM (Reach, Effectiveness, Adoption, Implementation, and Maintenance) framework³⁸ for evaluating the public health impact of this health policy change.⁴⁵ This framework builds upon the conceptual models of Rogers⁵⁶ and Green and Krueger⁵⁷ in this hybrid effectiveness-implementation study. A description of each of these measures and how they are applied to evaluating the successful implementation of a policy intervention are described in the table above. Effectiveness and Adoption measures are described in detail above. Implementation will be assessed by calculating a composite measure, or 'crude implementation index' for each facility as the sum of each secondary outcome (dichotomized at the median). We will conduct qualitative analyses of select dialysis facility providers that were successful intervention implementers ($n=5$) and non-

Table 2. Re-AIM Components and Study Measures to Track Implementation

RE-AIM Components	Definition	Study Measures
Reach	Number or % affected by policy; population characteristics	1. % of participating facilities with racial disparities / all facilities with racial disparities 2. Comparison of participating vs. non-participating facilities
Effectiveness	Change in outcomes	Primary outcome: Racial disparity in waitlisting
Adoption	Proportion that adopt policy or intervention	Secondary Outcomes: 1. Knowledge about allocation system 2. Staff training about transplant & allocation 3. Communication to patients 4. Intent to refer for kidney transplantation

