Implementation	Extent to which an intervention is delivered as intended	1. Crude implementation index 2. Qualitative analysis of implementers vs. non-implementers
Maintenance	Long-term behavior change	Longer-term (1-year) adoption measures among a subset of facilities

implementers (n=5). At 1 year via phone interviews. These providers will be selected among the providers who completed the follow-up survey and already provided consent for the intervention. Phone interviews will be recorded and transcribed to help us better understand how to improve the intervention for the future. Providers who participate in the interview will be given \$30 gift cards as an incentive.

Other Measures. To explore potential moderators of the effectiveness of this system-level intervention, we will examine facility characteristics (region, facility size, profit status, etc), characteristics of patients in facilities (e.g., race, SES, comorbidities, etc), and neighborhood characteristics. We will include process measures for the intervention (receipt of intervention and self-report) to evaluate utility, value, satisfaction and reactions to intervention materials to ensure optimal future dissemination of interventions to other US dialysis facilities.

STATISTICAL ANALYSES

We will evaluate our main outcome of change in AA vs. white racial disparity reduction in waitlisting in the year post-intervention compared to the year prior to the intervention among the intervention vs. control facilities (intent to treat) using generalized linear models⁴⁸ to account for potential correlation of facilities within Networks. Secondary analyses will examine facility- and patient-level modifiers of the intervention. Change in each of the secondary outcomes will be examined. *We hypothesize that increasing provider knowledge about the allocation policy in facilities with racial disparities will reduce waitlisting disparities.* Follow-up interviews will be transcribed verbatim and a codebook will be developed for qualitative analysis. Thematic analysis of key facilitators and barriers will be conducted to inform practice change.⁵¹

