Sample Size and Power. With 18 ESRD Networks participating (representing 1500 dialysis facilities with a waitlisting disparity), we estimate a minimum of ~375 facilities (average of 70 patients/facility) in each control/intervention group (total N=750), after accounting for ~1% loss from facilities that may close in the 1-year evaluation and yearly fluctuation in waitlisting disparity. This will achieve 80% power (at $\alpha=0.05$) to detect a difference of 10% in the waitlisting disparity ratio (%AA waitlisted/%white waitlisted) in the intervention vs. control group at 1 year, assuming the same disparity ratio (0.6) by group at baseline and an intraclass correlation coefficient of 0.06 among patients in a facility (based on RaDIANT). We found a 36% disparity reduction in the RaDIANT study after 9 months³¹; thus we expect that a 10% effect within 1-year is achievable.

DATA AND SAFETY MONITORING PLAN (DSMP) - A Dissemination Advisory Board (comprised of members of the SEKTC, and regional and national partners in the kidney transplant community) will be responsible for finalizing interventional material including performance feedback reports, webinars, and educational videos; See DSMB section in eIRB 81580.

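### The only power statement (80%) is for the AA/white waitlisting ratio at 1 year, but the primary outcome is defined as the pre/post change in the AA-white difference

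*Combined protocol and SAP*

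**What the plan says.** - **Effectiveness Measure Outcomes, item 1 (Primary Outcome):** "We will calculate facility racial disparity in waitlisting one year prior and post-intervention", and this is done "as the difference between the proportion of AA vs. whites waitlisted". That is a subtraction, taken before and after the intervention.
- **Statistical Analyses:** the intent-to-treat comparison concerns "our main outcome of change in AA vs. white racial disparity reduction in waitlisting", post-year against pre-year, intervention against control, by generalized linear models. No link function or effect scale is given.
- **Implementation effect measures and Table 2:** the effectiveness measure is simply racial disparity in waitlisting, with the remark "Effectiveness and Adoption measures are described in detail above". This points back to the difference.
- **Sample Size and Power:** 80% power at alpha 0.05, with a minimum of about 375 facilities per arm and 70 patients per facility, to "detect a difference of 10% in the waitlisting disparity ratio (%AA waitlisted/%white waitlisted) in the intervention vs. control group at 1 year". The division is written out, so the word ratio is not loose usage. Whether 10% means 0.60 to 0.66 or 0.60 to 0.70 is not said. The calculation rests on these inputs: "assuming the same disparity ratio (0.6) by group at baseline and an intraclass correlation coefficient of 0.06 among patients in a facility".

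No section gives power, a detectable effect or a standard deviation for the difference or its change.

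**The concern.** The sample size is justified for one quantity and the primary outcome is another. A ratio does not fix a gap: 0.60 to 0.70 is 2.0 points if 20% of white patients are waitlisted and 4.0 points if 40% are. The plan gives no race-specific rates and does not define its 10%, so it does not state what change in the AA-white gap the trial can detect.

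The two scales can also lead to different conclusions. The Introduction and Background names as an aim "to improve overall waitlisting rates and decrease disparities in kidney transplantation". If overall waitlisting rises, the ratio can improve while the gap stays the same. Because the model's effect scale is left open, the choice that decides the result could be made after the data are seen.

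**Working it through.** **Inputs.** Eligibility Criteria section: "AA (42.3%) and 53.0% white; mean age 61.7 years; 65.5% unemployed, 11.4% Medicaid insurance; and 25.8% of patients waitlisted". Sample Size and Power section: baseline ratio 0.6, ICC 0.06, 375 facilities per arm, 70 patients each, alpha 0.05 (taken as two-sided). Assumptions: the other 4.7% of patients are waitlisted at the AA-plus-white average; facilities are of equal size; the white rate is unchanged by the intervention; the correlation rho between a facility's AA and white effects is 0, 0.5 or 1.

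**Implied rates.** Let pW and pA be the white and AA proportions waitlisted.
- pW = 0.258 × 0.953 / (0.423 × 0.6 + 0.53) = 0.3137
- pA = 0.6 × 0.3137 = 0.1882
- Gap = 0.1255, or 12.5 points
- Patients per facility: 70 × 0.423 = 29.6 AA and 70 × 0.53 = 37.1 white

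The effect on the difference scale is (new ratio − 0.6) × pW: 3.1 points for 0.70 and 1.9 points for 0.66.

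**Variance.** Per arm, each proportion has variance p(1−p)[1 + (n−1) × 0.06] / (375n). The design effects are 2.72 (AA) and 3.17 (white). The AA-white covariance is rho × 0.06 × √[pA(1−pA)pW(1−pW)] / 375. Power = Φ(effect/SE − 1.96), with a delta-method SE for the log ratio.

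**The plan's own 80%.** For 0.60 to 0.70 at rho = 0, the log ratio is 0.154 and its SE 0.0540. Power is Φ(2.85 − 1.96) = 81.4%, close to the stated figure. This is only one reading. With a single design effect of 1 + 69 × 0.06 = 5.14, power is 56.6%. For 0.60 to 0.66 it is 41.4% at rho = 0 and 82.7% at rho = 1. The 80% cannot be uniquely reproduced.

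**Same effect on the difference.** For 0.60 to 0.70 at rho = 0, the SE is √[(3.74 + 4.19 + 2 × 4.90) × 10⁻⁵] = 0.0133. Power is Φ(0.0314/0.0133 − 1.96) = 65.4%. All cases, at 1 year only:

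| Target ratio | rho | Ratio power | Difference power |
|---|---|---|---|
| 0.70 | 0 | 81.4% | 65.4% |
| 0.70 | 0.5 | 93.3% | 82.5% |
| 0.70 | 1 | 99.8% | 98.5% |
| 0.66 | 0 | 41.4% | 29.5% |
| 0.66 | 0.5 | 56.1% | 41.5% |
| 0.66 | 1 | 82.7% | 70.0% |

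The difference detectable with 80% power is 2.80 × SE. With SE 0.0133, 0.0108 and 0.0076 this is 3.7, 3.0 and 2.1 points.

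**Scale effect alone.** Let k be the z-value on the difference divided by the z-value on the log ratio. Across the six cases k is 0.815 to 0.865. If ratio power is exactly 80%, difference power is Φ(2.80k − 1.96), which is 62.7% to 67.9%. An untransformed ratio gives 62.7% to 67.7%.

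**Change instead of 1 year.** A change score multiplies the variance by 2(1−r), where r is the unstated pre/post correlation. For 0.60 to 0.70 at r = 0.25, 0.50 and 0.75, difference power is 49%, 65% and 92% at rho = 0; 66%, 82% and 98% at rho = 0.5; and 92%, 98.5% and over 99% at rho = 1.

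**Can the scales disagree?** Add the same gain to both races until the ratio is 0.66. The white rate becomes 0.1255 / (1 − 0.66) = 0.3691, a gain of 5.5 points (5.2 to 5.8 if the other patients are waitlisted at anywhere from 60% to 0%). The gap stays at 12.5 points. The ratio test then favours the intervention in 45%, 60% or 86% of trials at rho = 0, 0.5 or 1 by formula (46%, 62%, 86% in a beta-binomial simulation of 3,000 trials). The difference test does so in 2.5% by formula and 2.5-2.7% in simulation, which is chance.

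**The case against.** The strongest reply accepts the mismatch but disputes its weight.

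- **The 1-year versus change contrast is minor.** With equal baseline ratios assumed, the expected contrast at 1 year equals the expected contrast in change. This stands: that half of the mismatch alters the variance, not the target. The ratio-versus-difference half does not depend on it.
- **Baseline adjustment would do better than a change score.** With a variance factor of 1 − r² and r = 0.5, difference power for 0.60 to 0.70 is about 78%, 92% and over 99% at rho = 0, 0.5 and 1. This also stands, and it shows that absolute power is open in both directions.
- **375 per arm is a minimum, and about 1,500 facilities are mentioned elsewhere.** At 750 per arm, difference power for 0.60 to 0.70 is 91.5% or more; for 0.60 to 0.66 it is 52%, 69% and 94%. But the protocol ties its 80% to 375 per arm, so a larger trial does not turn that figure into power for the difference.
- **The equal-gain case is not predicted anywhere.** Correct. It would be a relative rise of 29% in AA and 18% in white waitlisting (5.5/18.8 and 5.5/31.4). It shows only that the scales can diverge.
- **The gap can be back-calculated.** It can, to 3.1 or 1.9 points, but only by adding an assumption and choosing a meaning for 10%. The plan does neither.

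**Conclusion.** The concern holds on the text alone: the primary outcome is a change in a difference, the only power figure is for a ratio, and no section connects them or fixes the model's scale. The size of the scale effect is 63-68% power on the difference where the ratio has exactly 80%, assuming an unchanged white rate and the implied rates of 31.4% and 18.8%. Across the scenarios examined at 375 per arm, post-only difference power runs from 29.5% to 98.5%, depending mainly on the meaning of 10% and the AA-white correlation. No power shortfall is therefore established. What is established is that the sample-size justification does not apply to the defined primary outcome, and that leaving the scale open could change the trial's conclusion.

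**What to change.** 1. Keep the AA-minus-white difference, as written, as the single primary scale.
2. In Statistical Analyses, state that the model estimates the between-arm contrast in the pre/post change of that difference, and name the link.
3. In Sample Size and Power, restate power and the detectable effect in percentage points. Give the assumed AA and white rates, the AA-white facility-effect correlation, the pre/post correlation and the sidedness of the test, and say whether 10% is relative or absolute.
4. Make the ratio a supportive analysis, and report the AA and white proportions waitlisted by arm so that readers can see both scales.

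The cost is wording in two sections and one recalculation, using existing surveillance data or stated assumptions. The result may fall above or below 80%. Randomisation, follow-up and outcome data collection do not change.
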